Sample Size: Sample size calculation was based on the hypotheses associated with the Effectiveness component of RE-AIM and our prior research.^{8,10,12,22,23,29,77} With regard to facility level outcomes, our prior work resulted in effect sizes of 0.9 for environmental and policy changes.^{22,76,120} With the proposed sample size of 50 facilities, the statistical power for these two measures will be adequate (>.90 for both outcomes based on our analysis plan). For resident level outcomes, person-centered approaches resulted in a small intervention effect (Cohen's $d=0.19$) to maintain or improve BPSD, function, wellbeing or experiencing adverse events.^{8,10,12,22,23,29,77} Given a two-tailed alpha of 0.05, an estimated intra-class correlation coefficient (ICC) between clusters (facilities) of 0.02, a correlation coefficient between repeated measures (baseline, 4 and 12 months) of 0.6, and assuming even dispersion of means, a total sample of 500 residents will provide sufficient power ($\geq .80$) to detect the small effect size for group differences.¹²¹ Our prior research showed a 20% rate of attrition over 12 months.^{8,77} Therefore, we anticipate that a total of 625 residents from 50 nursing homes will be sufficient to demonstrate outcomes. To achieve this sample we will recruit 12-13 residents in each facility.

Setting: Nursing homes will be invited and eligible to participate if they: (a) agree to actively partner with the research team to change practice; (b) have at least 100 beds; (c) identify a RN, LPN or CNA to be the Champion; and (d) are able to access email and websites via a phone, tablet or computer. Recruitment of facilities will be done by mailing invitations to eligible facilities within the two states followed by telephone calls. We will also post invitations on relevant websites (see letters of support). This approach has been used successfully in our prior work.²² Fifty percent of the facilities we invited participated.²² Currently there are 152 nursing homes of appropriate size in Maryland and 439 in Pennsylvania. Given the regulatory climate with respect to dementia care in nursing homes, we are confident we will be able to engage 25 facilities per state.

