The hypothesis will be tested by evaluating the interaction term for each outcome variable. Similar LMMs will be used to compare changes in facility level measures (i.e., environments, policies) from baseline to 12 months with only facility included as random effects. For each hypothesis, exploratory analyses will be performed to assess model assumptions. Post-analysis diagnostic measures (e.g., residuals) will be explored to assess model fit. All tests will use a 5% significance level. The use of LMM will provide flexibility with regard to assumptions related to the covariance structure of the residuals and the presence of missing data for the repeated measures.¹⁵⁴ Missing data. In prior research we had 20% rate of attrition at the resident level and 10% of facilities.^{22,23} If there is significant dropout, we will identify baseline characteristics that differ between persons or facilities that drop out. Maximum likelihood methods will be used for primary analyses, which address non-informative dropout (missing at random [MAR]). If "informative" dropout appears possible, we will consider sensitivity analyses that involve adding these relevant baseline covariates to make the MAR assumption more plausible.¹⁵⁵ Qualitative data will be collected to inform effectiveness outcomes.

Adoption: Staff Adoption: Descriptive statistics will be done to evaluate the number of Internal Champions and Stakeholder team members participating in initial face-to-face training and monthly meetings among the 25 facilities randomized to EIT-4-BPSD. We will also consider improvement in scores on the Use of Behavioral Interventions for BPSD measure at each testing time point as evidence of adoption among staff. Facility Adoption: Facility adoption will be based on changes in environments, policies, and care plans of residents at 4 and 12 months post implementation of EIT-4-BPSD such that there is at least 1 item changed in each assessment area. Further we will describe differences among EIT-4-BPSD facilities that demonstrate adoption (based on changes in environments, policies and care plans) early (the first 4 months) versus late adopters (between 5-12 months) versus those that are non-adopters (no change by 12 months). Predictors such as facility characteristics will be compared across the three potential times of adoption (early, late, nonadopters).

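### The facility-level power of more than .90 depends on an SD basis and a correlation the plan does not state, and the sample size leaves out the 10% facility loss seen in prior work

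*Combined protocol and SAP*

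**What the plan says.** In section C (Approach), the Sample Size paragraph reports that "our prior work resulted in effect sizes of 0.9 for environmental and policy changes". It continues "With the proposed sample size of 50 facilities" and concludes that "the statistical power for these two measures will be adequate (>.90 for both outcomes based on our analysis plan"). The two measures are the Environment and Policy assessments, which carry most of hypothesis H2.

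The Data Analysis section sets the test: "Similar LMMs will be used to compare changes in facility level measures (i.e., environments, policies) from baseline to 12 months". The hypothesis is judged on the group-by-time interaction, and "All tests will use a 5% significance level". The Adoption paragraph refers to implementation "among the 25 facilities randomized to EIT-4-BPSD", so the split is 25 and 25.

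For residents, Sample Size gives more detail: "Given a two-tailed alpha of 0.05", an ICC of 0.02, a repeated-measures correlation of 0.6 and a requirement of 500 residents, raised to 625 for 20% attrition. The Missing data paragraph then states: "In prior research we had 20% rate of attrition at the resident level and 10% of facilities". The facility part of that sentence does not appear in Sample Size.

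**The concern.** A power figure can be checked only if the effect size and the test are on a known common scale. The effect is described in terms of changes and the test compares changes, so the plain reading puts both on the change scale. On that reading 50 facilities fall slightly short of .90. A reading on which the claim holds exists, but it needs a facility-level correlation, and the only correlation in the plan belongs to the resident outcomes.

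The sample size also treats the two kinds of attrition differently. Resident loss from prior research is built in. Facility loss from prior research is not, although losing a facility removes a unit from the H2 analysis and can remove its residents from H1.

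At stake is the risk of missing a true H2 effect of the assumed size, and whether the resident target of 500 completers has any margin.

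**Working it through.** **Inputs.** Effect 0.9, 50 facilities (25 per arm) and the 5% level are from the plan. Two-sided testing is stated for residents and assumed here for facilities. The 45 facilities are 50 × 0.90, split 23 and 22. The facility-level correlation ρ between baseline and 12 months is not given, so it is varied.

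**Formula.** Noncentral t with n₁ + n₂ − 2 degrees of freedom and noncentrality d / √(1/n₁ + 1/n₂). With two time points and complete data, the interaction test in the mixed model is the two-sample comparison of changes. Lost facilities are treated as contributing nothing. This is slightly pessimistic, since the model would keep their baseline values.

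**1. The plan's figure, 0.9 used directly (0.9 on change).**
- 25 v 25: noncentrality 0.9 / √(2/25) = 3.18, power 0.877. The normal approximation gives 0.889. Neither exceeds .90.
- 23 v 22: noncentrality 0.9 / √(1/23 + 1/22) = 3.02, power 0.839.
- Exceeding .90 needs d of about 0.936 with 50 facilities, 0.989 with 45, or 27 facilities per arm (0.901) at d = 0.9.

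**2. The same test, 0.9 on the score SD.** The effect on change is then d = 0.9 / √(2(1 − ρ)).

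| ρ | d on change | 50 facilities | 45 facilities |
|---|---|---|---|
| 0.3 | 0.761 | 0.75 | 0.70 |
| 0.4 | 0.822 | 0.81 | 0.77 |
| 0.5 | 0.900 | 0.88 | 0.84 |
| 0.6 | 1.006 | 0.94 | 0.91 |
| 0.7 | 1.162 | 0.98 | 0.97 |

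Power passes .90 at ρ of about 0.54 with 50 facilities and 0.59 with 45.

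**3. The 12-month score adjusted for baseline.** One further degree of freedom is used. The effective d is 0.9 / √((1 + ρ)/2) if 0.9 is on change, and 0.9 / √(1 − ρ²) if it is on the score SD.

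| Basis of 0.9 | d at ρ = 0.6 | 50 facilities | 45 facilities |
|---|---|---|---|
| Change SD | 0.9/√0.80 = 1.006 | 0.94 | 0.91 |
| Score SD | 0.9/√0.64 = 1.125 | 0.97 | 0.96 |

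The first d equals the ρ = 0.6 entry in step 2 only because 2(1 − 0.6) and (1 + 0.6)/2 are both 0.8.

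These results also depend on ρ. On the change basis, adjusted power falls as ρ rises: it stays above .90 up to ρ of about 0.85 with 50 facilities and 0.65 with 45. On the score basis it rises with ρ and passes .90 at about 0.28 and 0.42. At any ρ below 1, adjustment gives more power than the change test, apart from one degree of freedom.

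**4. Residents.**
- Plan: 500 / 0.80 = 625, which reproduces.
- 10% of facilities lost, and the 20% excludes residents lost with them: 625 × 0.90 × 0.80 = 450.
- The 20% already includes residents lost with their facility: 625 × 0.80 = 500.
- Keeping 500 in the first case would need 500 / (0.80 × 0.90) = 694.4, so 695 recruited.

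**The case against.** The strongest reply is that the stated power may be right. The plan ties the figure to its analysis plan, and it elsewhere uses the word changes for modifications made in a facility, so 0.9 may well be on the score SD. With ρ = 0.6 the planned test then gives 0.94, and still 0.91 with 45 facilities. This stands. A reader might infer that 50 facilities fail to deliver .90, or that the chance of missing the effect is 12% to 16%. The documents do not support that as a flat statement, because they leave the SD basis open. Equally, they do not establish the favourable reading, since 0.6 is stated only for residents.

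A reader might also infer that dropout will leave 450 residents. That is the lower end of the range. The plan does not say whether its 20% includes residents lost with a facility. Maximum likelihood would also keep residents with partial data in the analysis.

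Nor is the 10% a declared planning rate for this trial. It is prior experience, cited to work that the Preliminary Research section describes in assisted living. The 20% that the plan did apply is likewise prior experience, however. The waiting list covers volunteer facilities that decide not to take part; nothing says it replaces facilities lost during follow-up.

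Finally, the shortfall is small: one to two points with all 50 facilities on the change basis. Even 0.84 exceeds the .80 accepted for residents. That limits the weight of the point but does not make the stated figure verifiable.

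**Conclusion.** The point holds in conditional form. The claim of more than .90 rests on assumptions the plan does not state. For the planned change test, power is 0.88 with 50 facilities and 0.84 with 45 if 0.9 is standardised on change. If it is standardised on the score, the claim requires a facility-level correlation above about 0.54 or 0.59 respectively. The 10% facility loss from prior research enters neither the facility power nor the resident inflation. If it recurs, 450 to 500 residents would complete.

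These results assume two-sided 5% tests, equal allocation and nearly balanced facility loss. This is a gap in the stated assumptions and an avoidable loss of efficiency. It does not show that the trial is underpowered for H2.

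**What to change.** 1. Analyse the 12-month Environment and Policy scores with the baseline score as a covariate, in place of the group-by-time test of change. The baseline scores are already collected, so the cost is one line of analysis wording and no added facilities.
2. Restate facility-level power with its SD basis and assumed baseline-to-12-month correlation, for 50 and for 45 facilities. If the change test is kept and 0.9 is on change, the figures are 0.88 and 0.84. Show a range of correlations, because 0.6 is only an assumption for facilities.
3. State expected completing residents as 450 to 500 if 10% of facilities are lost, and say whether the 20% resident attrition includes residents lost with their facility.

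Items 2 and 3 are changes of text only. The stated power may look slightly less favourable unless item 1 is adopted.

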Descriptive statistics including measures of central tendency, dispersion and appropriate visualization approaches (e.g., box plots and spaghetti plots) will be performed on each outcome variable for residents and facilities. This will be done to ascertain distributional characteristics and ensure that the assumptions (e.g., normality) associated with the planned statistical procedures are met. When necessary, transformations will be performed. All analyses will be done using an intent-to-treat philosophy. Baseline characteristics (both resident level and facility level) will be compared between intervention and control groups and the relevant variables (e.g., age) that differ by group will be included as covariates in hypotheses testing. In particular we will utilize constructs known to correlate with BPSD including gender, pain, health status and cognitive and functional impairment. Linear mixed models (LMMs)¹⁵³ for longitudinal data (baseline, 4 and 12 months) will be used to assess the intervention effect on continuous outcomes (i.e., function, behavioral symptoms, and quality of life) accounting for clustering of residents that may occur within the same facility and correlations between repeated measurements of each resident. Mixed-effect Poisson regression [i.e., Generalized Linear Mixed Model

(GLMM)] will be conducted to assess the effect of the intervention on count outcomes (i.e., number of adverse events including number of falls, hospitalizations and emergency room visits, restraint use). The fixed effects included in the models will be treatment group (EIT-4-BPSD versus EO), time (baseline, 4 and 12 months), group-by-time interaction term and the aforementioned relevant covariates (e.g., age). Random effects will include facilities and residents.

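### The stated power of at least .80 at 500 residents does not belong to the group-by-time interaction test that the analysis section plans

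*Combined protocol and SAP*

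**What the plan says.** Methods, Sample Size, sets the resident-level inputs: two-sided alpha 0.05, Cohen's d = 0.19, ICC 0.02, correlation 0.6 between the baseline, 4- and 12-month measures, and "assuming even dispersion of means". From these it concludes that "a total sample of 500 residents will provide sufficient power" (at least .80) "to detect the small effect size for group differences". It cites a reference for the method but prints no formula. It does not say which visit or SD d refers to, or what pattern of means is meant. It then states "Our prior research showed a 20% rate of attrition over 12 months" and raises the sample to 625 residents in 50 facilities.

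Data Analysis, Aim 1, Effectiveness, describes a linear mixed model whose fixed effects include treatment group, "time (baseline, 4 and 12 months), group-by-time interaction term" and covariates. It adds: "Random effects will include facilities and residents". On the test it is explicit: "The hypothesis will be tested by evaluating the interaction term for each outcome variable". Under Missing data, "Maximum likelihood methods will be used for primary analyses". No comparison of follow-up scores adjusted for the baseline score is described.

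**The concern.** The power sentence names a group difference, while the analysis section tests whether the group difference changes over time. These are different contrasts with different variances, so a power figure for one does not carry over to the other.

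The sentence is the only quantitative basis for the resident sample of 500 analysed and 625 enrolled. If the planned test has materially less power than .80 at d = 0.19, a null resident-level result could be over-read. The plan implies at most a 20% chance of missing such an effect, and the true chance under the named test could be well above that.

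**Working it through.** **Inputs from Sample Size:** alpha 0.05 two-sided, d = 0.19, ICC 0.02, correlation 0.6, 500 analysed, 20% attrition, 50 facilities. Data Analysis gives 25 facilities in the intervention arm, hence 250 residents per arm and 10 per facility at 500.

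**Assumptions, because the plan does not define them:** SD = 1 at each visit; equal correlation between visits; d is the largest follow-up gap; no gap at baseline; time is categorical for the 2-df test. Two patterns of gaps at 0, 4 and 12 months are used: growing (0, .095, .19) and sustained (0, .19, .19). With a facility effect constant over time, as a facility random intercept implies, facility cancels from within-resident contrasts at 500 complete cases.

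**What reproduces.** 500/0.80 = 625 and 625/50 = 12.5 residents per facility. Both agree with the plan.

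**Power formulas.** One df: Φ(√λ − 1.96). Two df: noncentral chi-square with 2 df, critical value 5.99.

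**Planned interaction, 2 df.** λ = (250/2)/(1 − 0.6) × Σ(gap − mean gap)² = 312.5 × Σ(gap − mean gap)².
- Sustained: 312.5 × 0.02407 = 7.52, power 0.69.
- Growing: 312.5 × 0.01805 = 5.64, power 0.56.
- If facility effects vary over time, divide by 1 + 9 × 0.02 = 1.18: λ = 6.37 and 4.78, power 0.61 and about 0.48.

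**One-df forms of the interaction.**
- 12-month change, variance factor 2(1 − 0.6) = 0.80: λ = 0.0361/(2 × 0.80/250) = 5.64, power 0.66 under either pattern.
- Follow-up mean minus baseline, variance factor 0.80 + 1 − 1.2 = 0.60: sustained λ = 0.0361/0.0048 = 7.52, power 0.78; growing λ = 0.1425²/0.0048 = 4.23, power 0.54.

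**Unadjusted difference averaged over three visits** (one possible reading of group differences, with a gap of 0.19 at every visit). Variance factor (1 + 2 × 0.6)/3 = 0.733: λ = 6.15, power 0.70 without clustering. With the 1.18 design effect it is 0.63; with a constant facility variance of 0.02 it is 0.60.

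**Baseline-adjusted comparisons, not described in the plan.**
- Mean of both follow-ups adjusted for baseline, variance factor 0.80 − 0.36 = 0.44. Sustained: λ = 0.0361/(2 × 0.44/250) = 10.26, power 0.89 without clustering; 0.84 with the 1.18 design effect; up to 0.88 with a constant facility effect. Growing: λ = 0.1425²/0.00352 = 5.77, power 0.67 without clustering and 0.60 to 0.65 with it.
- 2-df test with baseline means constrained equal, constant facility effect: λ = 9.72 and power 0.80 sustained; λ = 6.88 and power 0.65 growing.

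| Test at 500 complete cases | Growing | Sustained |
|---|---|---|
| Interaction, 2 df | 0.56 | 0.69 |
| 12-month change | 0.66 | 0.66 |
| Follow-up mean minus baseline | 0.54 | 0.78 |
| Baseline-adjusted follow-up mean (with ICC) | 0.60–0.65 | 0.84–0.88 |
| 2 df, baseline constrained equal (with ICC) | 0.65 | 0.80 |

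**625 enrolled, 20% lost, maximum likelihood** (all losses before month 4, or all between months 4 and 12). The 2-df interaction has 0.58–0.59 growing and 0.71–0.77 sustained; 12-month change has 0.68–0.69. Follow-up mean minus baseline has 0.56–0.61 growing and 0.81–0.85 sustained.

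**Detectable d with .80 power at 500.** The 2-df test needs λ = 9.63, so d = 0.19 × √(9.63/7.52) = 0.215 sustained and 0.19 × √(9.63/5.64) = 0.248 growing. For 12-month change it is 0.224. For follow-up mean minus baseline it is 0.194 sustained and 0.259 growing.

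**The case against.** The strongest reply is that .80 does follow from the stated inputs at exactly 500. A baseline-adjusted difference in the mean of both follow-ups gives 0.84 to 0.88 with clustering included, and the Sample Size paragraph speaks of group differences without saying that three visits are averaged. This stands. It rules out two stronger conclusions that a reader might draw: that the inputs cannot yield .80, and that the gap has some cause beyond the choice of test. Choice of contrast, together with the pattern of effect, can account for all of it. The three-visit average is only one reading, and an odd target in a randomised trial, where no baseline gap is expected. What the reply does not do is rescue the plan as written: the Data Analysis section describes neither baseline-adjusted test, and both fall to 0.60–0.65 with clustering if the effect grows evenly.

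Second, the method reference is not available here, and d, its SD and the pattern of means are undefined. Failure to reproduce is therefore not proof of a slip in arithmetic, and the sums that are printed are correct. This also stands.

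Third, entering f = d/2 = 0.095 as an interaction effect size in a repeated-measures calculation gives λ = 0.095² × 500 × 3/0.4 = 33.8 and power above 0.99. But that f corresponds to a follow-up gap of √(0.0361 × 4.5) = 0.40 SD sustained or √(0.0361 × 6) = 0.47 SD growing, more than twice 0.19. It would explain a high figure without supporting it for d = 0.19.

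Finally, follow-up mean minus baseline comes within two points of .80 at 500 for a sustained effect (0.78), and exceeds it with 625 enrolled under maximum likelihood. That is fair, but the plan names neither that contrast nor that pattern, and its claim is made for 500.

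**Conclusion.** The point holds as a mismatch between the power statement and the planned test. Under the assumptions listed, the 2-df interaction has a 31% to 44% chance of missing a true d = 0.19 at 500 complete cases, against the 20% at most that the plan implies. It is worse if facility effects vary over time. None of the interaction forms tabulated reaches .80 at 500.

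Confidence is moderate, because the size depends on what d and the pattern of means are taken to be. If even dispersion means equally spaced gaps, the growing column applies and no test in the table reaches .80. If the effect is sustained, the baseline-adjusted tests do. The documents do not settle which was meant. A reader might also infer that the trial needs more residents; the documents do not support that, since the same 500 suffice for a baseline-adjusted comparison under a sustained effect.

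**What to change.** Either of two changes would make the plan and its power agree.

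- **Keep the interaction test.** In Sample Size, restate the power, or the d detectable with .80 power, for the contrast that Data Analysis will test. For the 2-df test at 500 complete cases the detectable d is about 0.215 (sustained) to 0.25 (growing). In Data Analysis, add one sentence naming the contrast and saying whether time is categorical.
- **Keep the .80.** If it came from a baseline-adjusted follow-up comparison, name that comparison in Data Analysis as the test, before outcome data are examined, and state that the figure assumes a sustained effect.

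In either case, define d (which visits, which SD), say what pattern of means is assumed, and state the analysed sample (500 complete cases, or 625 enrolled under maximum likelihood) and the facility-effect assumption. If the sponsor's calculation used another meaning of d, print it with its inputs.

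The cost is a rewritten paragraph and a sentence. No added enrolment is proposed. The downside of the first option is a probably less favourable stated figure; the second changes the planned test and ties the claim to one effect pattern.

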Real World Experience and Pilot Testing EIT-4-BPSD: Our team has expertise with regard to clinical work ([name], [name], [name]), administration ([name]) and regulations ([name]), and implementation of relevant innovative approaches to care (all investigators) in nursing homes. In addition, we have expertise in the education of minorities and nursing assistants([name], [name], [name], [name], [name]) and using qualitative methods ([name], [name], [name]) (see biosketches). We have pilot tested the EIT-4-BPSD in two facilities (one in Maryland and one in Pennsylvania) for feasibility and demonstrated that sites are willing to identify a Champion and Stakeholder team, engage in monthly face-to-face meetings (100% participation of stakeholders) and weekly email interactions (100% participation). We implemented all components of the intervention, recruited residents (recruitment rate of 50%) and completed measures without being burdensome to residents or staff. Building on our extensive preliminary work we will test EIT-4-BPSD in 50 nursing homes in Maryland and Pennsylvania.

Methods

Design: To achieve our Aims we will use a Hybrid III pragmatic cluster randomized clinical trial³² for two reasons: (a) implementation of EIT-4-BPSD requires a facility-wide approach; and (b) we need to prevent treatment contamination that might occur if we randomized within sites. Fifty nursing homes will be randomized to treatment (EIT-4-BPSD) or Education-Only Control (EO) using permuted-block randomization. Assignment will be concealed until after the facility consents to participate. Outcomes at the resident and facility level will be evaluated. Resident outcomes will be obtained at baseline, 4 and 12 months post implementation of the intervention. Facility outcomes will be obtained at baseline and 12 months post initial implementation. We will also examine Maintenance in EIT-4-BPSD facilities at 24 months post implementation.

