Once the nursing facility expresses an interest in participating in the study, the facility will be randomized to one of three cohort groups and then randomized to EIT-4-BPSD or EO. We will implement EIT-4-BPSD in 8-10 facilities and the EO intervention in 8-10 facilities during each cohort period. We recognize there will be a period of time between recruitment and implementation of study related activities and will keep facilities updated. In addition, we will maintain a waiting list of interested facilities in the event that some volunteer facilities decide not to participate (their data will be included in terms of Reach).

Resident Participants: We will keep our resident enrollment criteria to a minimum to increase external validity. Residents will be eligible to participate if they: (a) are living in a participating nursing home; (b) are 55 years of age or older; (c) have a history within the past month of exhibiting at least one BPSD; (d) have cognitive impairment as determined by a score of 0-12 on the Brief Interview of Mental Status (BIMS);¹²² (e) are not enrolled in Hospice; and (f) are not in the nursing facility for short-stay rehabilitation care. We will obtain a list of all eligible residents from a designated staff member and randomly approach each resident until 12-13 residents per facility are recruited by research assistants (RAs) (N= 625 residents). This sampling approach is used to assure variability and equal participation from each nursing facility in the study. Based on our prior research and recent data from the most recent Nursing Home Compendium¹²³ we conservatively anticipate that 25% to 30% of residents will be eligible.^{123,124} We are confident we will be able to recruit 12-13 residents per facility.^{8,77,125} See the Human Subjects section for details of the consenting and recruitment process.

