Following this initial face-to-face training, each EIT-4-BPSD facility will be visited monthly for a total of 12 months by a Research Nurse Facilitator who works with the Champion and Stakeholder Team to implement EIT-4-BPSD (Table 2). This will be accomplished using the 4-step process delineated above. During monthly meetings (approximately 1-2 hours each) the Research Nurse Facilitator will explore challenges, celebrate successes and give feedback to the Stakeholder Team based on available pragmatic measures (changes made in the environment, policies, care planning) and will work with the Champion and staff to facilitate the implementation of components of EIT-4-BPSD (e.g., help with education, care plan development). Monthly interactions will intentionally allow the Stakeholder team to make revisions to the implementation process so that EIT-4-BPSD is standardized yet individualized for each facility. We will keep minutes of these meetings to describe the implementation process in each facility. This cyclic feedback pattern of review of progress and challenges will help guide staff intervention activities to best respond to contextual changes in the facility over time. In addition to the monthly visits, weekly emails will be sent to all Stakeholder Team members within the cohort to provide BPSD Tidbits. The Tidbits (examples provided in Appendix D) will include updates about person-centered behavioral approaches for BPSD and will share individual facility successes. To motivate stakeholder teams across the cohort, contests will be held (e.g., winning example for overcoming a challenging bathing interaction with a resident with BPSD) and winners announced in the weekly emails. In addition, we will use a pragmatic coaching model which has successfully improved up-take of innovation in long term care facilities.¹²⁹ This model involves having Champions sign up for weekly office hours with the Research Nurse Facilitator for individualized phone coaching sessions. Sessions will be up to 30 minutes and will be made at times convenient for the Champion during their workday. To motivate and retain the Champions we will provide them with a 50 dollar gift certificate to buy activity supplies/resources to engage residents with BPSD (e.g., games or music), and provide conference registration for each champion to attend the annual American Medical Directors Association or the International Counsel of Active Aging conference (see support letters).

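### A facility's arm is concealed only until facility consent, and nothing in the supplied text closes the staff-made list of eligible residents first, so H1 is exposed to a possible post-allocation selection effect of unknown size

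*Combined protocol and SAP*

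**What the plan says.** All references are to the combined protocol and SAP, section C, Approach.

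- **Methods, Design:** "Assignment will be concealed until after the facility consents to participate". No other event is named as ending concealment.
- **Methods, Setting:** once a home expresses interest, "the facility will be randomized to one of three cohort groups and then randomized to EIT-4-BPSD or EO".
- **Methods, Resident Participants:** "We will obtain a list of all eligible residents from a designated staff member and randomly approach each resident", until 12-13 per home are recruited by research assistants. Criterion (c) is to "have a history within the past month of exhibiting at least one BPSD". The paragraph ends "See the Human Subjects section for details of the consenting and recruitment process"; that section is not in the supplied text.
- **Table 3, months 1-4 (Cohort 1 set-up):** planning of EIT-4-BPSD training, an email list for champions and stakeholders, and planning of the in-service for Education Only (EO). The email list serves an EIT-4-BPSD activity: "weekly emails will be sent to all Stakeholder Team members within the cohort to provide BPSD Tidbits".
- **Table 3, months 5-17:** resident recruitment appears here, within each arm's intervention row. Cohorts 2 and 3 are said to follow the Cohort 1 process.
- **Procedure for Assessing Outcomes:** the research assistants who collect outcomes are blind to condition. Nothing similar is said of the staff member who supplies the list.
- **Data Analysis, Effectiveness:** baseline variables that differ between arms become covariates, and H1 is tested by the group-by-time interaction.

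**The concern.** When facilities are randomised but residents are enrolled individually, randomisation balances the residents only if enrolment cannot respond to the arm. Here the list is made inside the facility, by someone not said to be blind, and apparently at a stage when arm-specific planning may already have begun. Criterion (c) depends partly on what staff notice or record, and a list meant to be complete may not be. If staff in one arm list more, fewer or different residents, the residents studied could differ by arm in ways that randomising homes does not remove.

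The planned safeguards act later. Random approach samples only from residents already listed. Blinded assessors measure whoever has been enrolled. Covariate adjustment reaches measured variables only. At stake is the resident comparison, H1, and not necessarily every outcome in it equally.

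**Working it through.** **1. The plan's own recruitment figure.** Sample Size asks for 500 evaluable residents with 20% attrition: 500 / (1 - 0.20) = 625, and 625 / 50 = 12.5 per home. This reproduces the stated 625 and 12-13.

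**2. When implementation starts.** Table 3 dates the maintenance visits, so time zero can be worked back:

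- Cohort 1: 23 - 18 = 5 and 29 - 24 = 5
- Cohort 2: 39 - 18 = 21 and 45 - 24 = 21
- Cohort 3: 55 - 18 = 37

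These are the opening months of the three intervention blocks (5-17, 21-33, 37-49). Resident recruitment is shown only in those blocks, not in set-up (1-4, 18-20, 34-36). Table 3 does not say when staff are told the arm, or when within a block the list is made.

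**3. How far random approach protects.** Assume a full 100-bed home (the minimum size), the stated 25% to 30% eligible, and the pilot's 50% recruitment rate (two homes, denominator not stated). Then 25 to 30 residents are eligible, and 12.5 / 0.5 = 25 must be approached, which is 25/30 = 83% to 25/25 = 100% of the list. In the smallest homes the list nearly determines the sample. In larger homes, random approach gives a random sample of whatever list was made.

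**4. What the interaction test removes.** A baseline shift that stays constant cancels in the group-by-time contrast. One that fades does not. As an illustration only, suppose a selection shift of s SD fades in line with the plan's repeated-measures correlation of 0.6. The contrast is then off by (1 - 0.6) × s:

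| Assumed shift s (SD) | Error in contrast (SD) | Share of design effect 0.19 |
|---|---|---|
| 0 | 0 | 0% |
| 0.05 | 0.02 | 11% |
| 0.10 | 0.04 | 21% |
| 0.20 | 0.08 | 42% |

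The documents give no value for s.

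**5. How coarse a baseline check would be.** The plan does not say how a difference between arms is judged. Assume a two-sided 5% test with 625 residents, 50 homes and "an estimated intra-class correlation coefficient (ICC) between clusters (facilities) of 0.02":

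- Design effect: 1 + (12.5 - 1) × 0.02 = 1.23
- SE of a baseline difference: sqrt(4 × 1.23 / 625) = 0.089 SD
- Flagging threshold, t(48) = 2.011: 2.011 × 0.0887 = 0.178 SD (0.161 at ICC 0; 0.202 at ICC 0.05)
- Chance of flagging, noncentral t with 48 df: 19.7% for a true shift of 0.10 SD, 55.5% for 0.19 SD

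These figures describe such a check. They do not estimate the bias.

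**The case against.** The case on the other side is substantial.

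- **The missing section.** Listing order would naturally be set in the Human Subjects section, which was not supplied. This stands, and it makes the point conditional.
- **Table 3 is a coarse summary.** Disclosure timing is inferred. Every home must name a champion to be eligible, so identifying champions reveals no arm. The Cohort 2 and 3 set-up rows have no EO item, and face-to-face training there need not mean EIT-4-BPSD, because EO education may also be face to face. The clear evidence of arm-specific set-up is therefore Cohort 1 only. This stands.
- **Discretion is narrow.** Age, BIMS score, hospice and short-stay status leave little judgement. Criterion (c) needs one symptom in a month, and Significance puts such symptoms at up to 90% of residents with dementia. This stands, and leaves list completeness as the main route.
- **The motive is weak.** Table 2 reviews care plans of consented residents in EIT-4-BPSD homes, which might give staff in one arm a reason to think of particular residents. But the intervention is facility-wide, and Reach counts care plans of all residents in those homes, so a resident need not be listed to receive the approach. This weakens the motive considerably.
- **The model helps.** Baseline symptoms are a time point in the mixed model, so a stable shift is handled without covariate selection. The plan's named covariates can also be read as adjusted for whatever a test shows. Both stand; a fading shift remains.

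None of this supplies a rule that the list is closed before disclosure.

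**Conclusion.** The point holds as a gap in the stated order. Concealment is tied to facility consent alone, and the supplied text allows the resident list to be made with the arm known. The exposure is confined to H1. Its size and direction cannot be determined from the documents, and it may be zero. The contrast errors in the table rest on assumed shifts and an assumed pattern of fading, and the detection figures on an assumed 5% test.

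A reader might go further and infer that staff in all three cohorts will know the arm when they list residents, that listing will differ by arm, or that H1 is biased. The documents do not support any of these. No row says when staff are told, the arm-specific set-up work is clear only for Cohort 1, and nothing shows that listing would respond to the arm. The change is worth making because it is cheap and because selection on unmeasured features cannot be repaired in the analysis. If the Human Subjects section already fixes the order, only alignment is needed.

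**What to change.** - **Design:** extend the concealment sentence so that it also requires the facility's dated list of eligible residents to be closed.
- **Resident Participants, suggested wording:** *In the last month of set-up the designated staff member supplies a dated list of every resident meeting criteria (a)-(f) on that date. The list is closed before the facility learns its arm. Blinded research assistants approach listed residents in random order. If the list runs out, residents from a later list are flagged and H1 is repeated without them. Numbers listed, approached and consented are reported by arm.*
- **Table 3:** in each set-up row add *close resident list, then disclose arm to facility*. The research team may plan for either arm beforehand. The arm may still be generated at expression of interest; only disclosure moves.
- If the Human Subjects section already sets this order, align Methods and Table 3 with it.

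**Cost.** The trial already needs a list from each home (16-20 homes per cohort), so this is a re-ordering plus a few sentences. The downsides are:

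- Facilities have less planning time after disclosure.
- The past-month criterion is about 1 month old at time zero (5 - 4, 21 - 20, 37 - 36). Closing the list at the start of set-up would make it up to 4 months old in Cohort 1 (5 - 1) and 3 months in Cohorts 2 and 3 (21 - 18, 37 - 34), hence the last set-up month.
- The smallest homes may need a second list after disclosure: 13 / 0.5 = 26 approaches against 0.25 × 100 = 25 eligible, under the assumptions above. This partly reopens the route, hence the flag and repeat analysis.
- Resident consent may still follow disclosure, so the change protects the listing step only.
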